## **3. STUDY HYPOTHESIS/OBJECTIVES**

## 3.1 Primary objective

To determine whether BNZ reduces the composite primary outcome (death; resuscitated cardiac arrest; sustained VT; new insertion of pacemaker or ICD/CRT; cardiac transplantation; and development of new heart failure, stroke, or systemic thromboembolic events), compared to placebo in patients with CCC.

We will address the primary objective through the following hypotheses:

Ho: HRBNZ/Placebo =1

Ha:  $HR_{BNZ/Placebo} \neq 1$ 

The null hypothesis (Ho) can be rejected if the two-sided p-value is less than 0.05. We will consider BNZ is superior to placebo if the upper bound of the two-sided 95% confidence interval (CI) around  $HR_{BNZ/Placebo}$  is less than 1.

## 3.2 Secondary objectives

The secondary objectives are the following:

- To determine the effects of BNZ compared to placebo regarding negativization of PCR in patients with chronic CCC after 60-80 days of treatment and at 24 months and end of follow-up.
- To evaluate whether BNZ prevents new development of any of the following echo changes; segmental wall motion abnormalities, ventricular aneurysm, reduction in LV ejection fraction > 5%, increase in LVEDD > 5.0 mm compared with baseline.
- To evaluate whether BNZ prevents new 12 lead ECG alterations (complete bundle branch block, fascicular block, advanced atrio-ventricular block, atrial fibrillation(AF), etc).
- To evaluate whether BNZ prevents the progression of NYHA functional class by at least one category.
- To evaluate the safety, tolerability and adherence to BNZ in patients with CCC.

## 4. POPULATIONS TO BE ANALYZED

### 4.1 Intention-to-treat Population

All patients who are randomized are included in the analysis according to the treatment groups to which they were randomized, irrespective of whether or not the patient actually received study drug, the patient's compliance with the study protocol or duration of the trial participation. All analyses of primary and secondary endpoints, as well as baseline summaries, subgroup analyses and all analyses related to safety will be based on the intention-to-treat(ITT) principle. Sensitivity analyses for the primary and secondary outcomes will be performed based on the following two sub population A and B.

### 4.2 On-Treatment Population A

Population on treatment A (1543 Patients randomized from November 2004 to December 2008) is defined as:

Patient randomized to BNZ or placebo 5mg/kg/day for 60 days.

## 4.3 On-Treatment Population B

Population on treatment B(1312 Patients randomized from January 2009 to October 2011)

is defined as:

Patients randomized to BNZ total daily dose of 300 mg during 40 to 80 days depending on the patient's total weight); max dose 24 g for 80 Kg.

## **5. BASELINE CHARACTERISTICS**

Summary statistics for demographic data and baseline characteristics using ITT population will be displayed separately by the BNZ and placebo.

For categorical variables, summaries will consist of counts and percentages, with p-values comparing groups from chi-square tests. Note Fisher exact tests will be substituted for chi-square tests where expected counts are <5 per group.

For continuous variables, summaries will consist of means and standard deviations (SDs) with p-values comparing groups from t-tests.

For non-normally distributed variables including time duration variables which are not likely to be normally distributed, summaries will consist of median and percentiles 25th, 75th, with p-values comparing groups from Wilcoxon rank sum tests.

Demographic Characteristics include age, gender, weight, height, heart rate and blood pressure, country. Data for the background characteristics will be collected for education, smoking lifestyle,

alcohol use, employment status, occupation, and housing conditions. Baseline characteristics will include the following:

- Medical history: NYHA function class, previous admission due to heart failure, resuscitated cardiac arrest, sustained VT, internal cardiac defibrillator, atrial fibrillation, pacemaker, stroke/TIA, pulmonary embolism, systemic embolism, syncope, HIV, leukemia or lymphoma, tuberculosis, cancer
- Use of medications: Loop diuretic, Spironolactone, other diuretics, ACE-I, ARB, digoxin, aspirin, beta-blocker, amiodarone, other anti-arrhythmic, oral anticoagulants, antiplatelets
- Baseline ECG results: Normal/abnormal, electrocardiograms
- Chest X-ray: Cardio thoracic ratio > 0.59, signs of pulmonary congestion
- Lab results: WBC count, hemoglobin, platelet count, ALT/TGP, AST/TGO, creatinine
- 2D echocardiogram: LV ejection fraction, LV end-diastolic diameter, LV percent fractional shortening, LV thrombus regional wall-motion abnormalities, aneurysm
- Socio-demographics: Income, education, employment status, occupation, country
- Current housing conditions

## **6. COMPLIANCE**

Patient compliance will be categorized as good (>75%), medium (50-75%), or poor (<50% of taking study medication) and presented by treatment group. The frequency of subjects experiencing study drug interruption, the reasons for the interruption will be summarized by treatment group. The proportion of patients who were lost will be reported.

## 7. STUDY FOLLOW-UP TIME AND MISSING DATA

## 7.1 Study follow-up time

Overall follow-up for the BENEFIT Trial will be in average 5.5 years. Active follow-up will be planned during the intervention period that lasts between 40 to 80 days. During this period safety, tolerability and adherence visits are programmed at 11 and 21 days and at the end of therapy (40 to 80 days). The next visit will be at 6 months for the detection of clinical outcomes. Yearly follow-up visits are programmed until study termination at a mean time of 5.5 years. The duration of the follow-up will be summarized by treatment group.

All efforts will be made to collect information related to the clinical outcomes for those participants lost to follow-up. In case of written withdrawal of consent for follow-up visits, and unless otherwise stated by the patient in the informed consent form, investigators will be encouraged to get information from the general practitioner, any other physician or other medical-care provider, or from patient relatives in order to follow the medical status of the patients (especially when they withdrew their consent after having experienced an adverse or serious adverse events). In case of no contact and missing information on the efficacy assessment, the patient will be censored on the last day of available contact during the study.

For a single event like death the date of event will be defined as the date reported on event CRF. The date of events with potential multiple episodes such as cardiac arrest or stroke will use the date of the first episode. For composite outcomes, the date of the first occurring component will be used as the date of the event. The date of final follow-up will be defined as the last date among all dates of visits/contact and dates of events reported on the event report forms or any laboratory test dates.

In a time-to-event analysis, the survival time will be calculated as the date of event minus date of randomization plus 1 for a patient with an event. For those without an event, the survival time will be the date of final follow-up minus date of randomization plus 1.

## 7.2 Missing data

Missing data will be vigorously pursued with the quality assurance process. Centres will be requested to collect as much information as possible. In general missing values will be treated as missing, unless otherwise specified. Unknown data will be coded as such in the database and classified as such on any analysis. No attempt will be made to impute missing values and only observed values will be used in the analyses. Depending on the assessment, analyses may not include all patients in an analysis population, because certain patients in the intended population may have missing data.

Patient mortality and morbidity will be determined for all participants regardless of compliance with study medication or visit schedule. For patients who die prior to follow-up evaluation of LV function or ECG, and worse case rank will be assigned to that patient and a secondary non-parametric analysis will be done to examine the sensitivity to these missing data.

## **8. EFFICACY ANALYSIS**

## 8.1 Definition

8.1.1 Primary Outcome

The primary efficacy outcome is defined as the first occurrence of any of the following clinically significant outcomes at follow-up in patients with CCC

- i) Death
- ii) Cardiac arrest, requiring defibrillation or cardioversion
- iii) Documented spontaneous sustained ventricular tachycardia requiring or not electrical or pharmacological cardioversion

- iv) New or worsening symptomatic congestive heart failure with at least two predetermined criteria (signs and symptoms of CHF, Chest X-Ray with fondings compatible with CHF, need for intravenous therapy, or new initiation of diuretics, hospital admission due to HF)
- v) Pacemaker or implantable cardiac defibrillator/CRT implantation
- vi) Heart transplant
- vii) Stroke or systemic embolism (including pulmonary embolism)
- viii)

Efficacy variables will be recorded at baseline and after termination of the 80 day course of therapy. Similarly, efficacy parameters will be recorded at month 6, year 1 to 9 and final visits. Investigators will be instructed to complete CRFs and inform of any outcome event within 2 days of their knowledge, or at specified study visit dates. Analysis of efficacy variables will be performed at the different times of collection of these variables as well as at the end of follow-up.

### 8.1.2 Secondary Outcome

The secondary efficacy outcomes are the following separate individual events:

- Negativization rate of PCR based on baseline and follow-up qualitative PCR result between patients receiving benznidazole compared to placebo.
- Negativization of *T. cruzi* parasite load detected by competitive PCR: Parasitic load is expressed as the amount of *T. cruzi*/ml of blood between patients receiving benznidazole compared to placebo.
- New development of any of the following echo changes; segmental wall motion abnormalities, ventricular aneurysm, reduction in LV ejection fraction > 5%, increase in LVDD > 5.0 mm compared with baseline.
- New 12 lead ECG alterations (complete bundle branch block, fascicular block, advanced atrio-ventricular block, atrial fibrillation, etc).
- Progression of NYHA functional class by at least one category

Other analysis will include regional variation of CCC progression, primary and secondary outcomes in PCR [+] and PCR [-] subjects at baseline.

*T. cruzi I* vs *T.cruzi II* primary and secondary outcomes as described above.

## 8.2 Analysis Method

All cardiovascular outcome assessments will be reviewed by an Event Adjudication Committee (EAC), who will be kept blinded to the treatment assignment of participants. All statistical analyses of these outcomes will be based upon adjudicated outcomes, where applicable. In case that an adjudicated result is not available, the clinical investigator's assessment will be accepted. A two-sided significance level of 0.05 will be used for overall analysis. No adjustments for multiplicity will be made for multiple efficacy endpoints.

#### 8.2.1. Analysis of primary outcome

The primary efficacy outcome (composite of death; resuscitated cardiac arrest; sustained ventricular tachycardia; new insertion of pacemaker or ICD/CRT; cardiac transplantation; and development of new heart failure, stroke, or systemic thromboembolic events) will be analyzed using a time-to-event approach, counting the first occurrence of any component of the composite outcome. Censoring will occur if the patient is lost to follow-up or reaches the end of the followup period without experiencing the primary outcome. Patients who prematurely discontinue their follow-up visits prior to the development of primary composite outcomes will be censored as of their last completed follow-up visit. The treatment groups will be compared on each secondary efficacy outcome. Cumulative incidence curves over time for each treatment group will be provided using the product limit estimation method and compared using a logrank test. Treatment comparison based on Cox proportional hazard model will be reported as hazard ratio (HR) and 95% confidence interval (CI). The proportionality assumption of the Cox regression model will be assessed graphically and with the use of Schoenfeld residuals, or by including a time-treatment interaction term in the Cox model (time log transformed). The number and incidence of each component of the composite primary outcome will be summarized in each treatment group. For the subgroup analysis (see section 10), test for interaction will be based on Cox regression by including an interaction term with treatment in the model.

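### SAP 8.2.1 censors patients who stop attending at their last completed visit, in conflict with the last-contact rule in SAP 7.1 and the outcome follow-up promised in SAP 7.2

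*Supplement*

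**What the plan says.** The SAP gives two rules for ending a patient's time at risk.

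- **Section 8.2.1 (analysis of the primary outcome).** Patients who stop attending before a primary event "will be censored as of their last completed follow-up visit". The sentence before it censors patients who are lost, or who reach the end of follow-up, without a primary event.
- **Section 7.1 (follow-up time).** Outcomes are still pursued once visits cease: "All efforts will be made to collect information related to the clinical outcomes for those participants lost to follow-up". After written withdrawal from visits, and unless the patient has said otherwise, "investigators will be encouraged to get information from the general practitioner, any other physician or other medical-care provider, or from patient relatives". Only where there is no contact and efficacy information is missing does it say that "the patient will be censored on the last day of available contact during the study". It also fixes the end of observation: "The date of final follow-up will be defined as the last date among all dates of visits/contact and dates of events" (laboratory dates count too). Survival time is computed from the event date for patients with an event and from this final date for the rest.
- **Section 7.2 (missing data).** "Patient mortality and morbidity will be determined for all participants regardless of compliance with study medication or visit schedule".
- **Section 4.1 (ITT population).** Everyone randomised is analysed as randomised, irrespective of "compliance with the study protocol or duration of the trial participation".

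Neither the SAP nor the protocol says which censoring rule takes precedence.

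**The concern.** The rules give different data for the same patient, in the primary endpoint. Two programmers working faithfully from this SAP could produce different event counts and hazard ratios, and the choice between them might be made after the results are known.

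The 8.2.1 rule is also the weaker one. Patients may stop attending because they are getting worse. If their later deaths and heart-failure events are known but set aside, censoring depends on prognosis, which the log-rank test and the Cox model assume it does not. Information that sites were asked to collect would go unused.

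**Working it through.** The documents state no figure for the effect of this rule, so there is none to reproduce. The check is first textual. The arithmetic after it gives scale only.

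**Step 1. Two hypothetical patients under each rule.**

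| Patient | SAP 7.1 and 7.2 | SAP 8.2.1, read literally |
|---|---|---|
| Stops visits in year 2, known to have died in year 4 | Event in year 4 | Censored in year 2 |
| Stops visits in year 2, confirmed event-free by telephone in year 5 | Censored in year 5 | Censored in year 2 |

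The rules disagree for both.

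**Step 2. Events beyond the last visit.**

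Inputs from SAP section 2: N = 2753, control rate 8% per year, mean follow-up T = 5.5 years, 26.5% reduction (HR 0.735). Allocation is 1:1 (protocol 4.2.3). The protocol's effect is a 20% reduction (protocol 4.1), taken here as HR 0.80.

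Assumptions, not in the documents: a share d = 5%, 10% or 20% stop visits, at times spread evenly over follow-up; the hazard is constant and unchanged after stopping; every later event could be found. The 20% borrows the drop-out figure in protocol 4.1, which is not defined as stopping visits.

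With hazard λ, the probability of an event by T is p = 1 − exp(−λT). The average probability of an event before an evenly spread stopping time is q = 1 − p/(λT).

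- Control: λT = 0.44, p = 0.356, q = 1 − 0.356/0.44 = 0.191
- HR 0.735: λT = 0.3234, p = 0.276, q = 0.146
- HR 0.80: λT = 0.352, p = 0.297, q = 0.157

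All events = (2753/2) × (sum of the two p): 870 at HR 0.735 and 898 at HR 0.80. Events lost = d × (2753/2) × (sum of p − sum of q).

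**Step 3. Power.** Schoenfeld, two-sided 0.05: Φ(|ln HR| × √D / 2 − 1.96), with D the events kept.

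| d | Lost, HR 0.735 | Power | Lost, HR 0.80 | Power |
|---|---|---|---|---|
| 0 | 0 of 870 | 99.5% | 0 of 898 | 91.7% |
| 5% | 20 (2.3%) | 99.4% | 21 (2.3%) | 91.1% |
| 10% | 41 (4.7%) | 99.3% | 42 (4.7%) | 90.4% |
| 20% | 81 (9.4%) | 99.1% | 84 (9.3%) | 89.0% |

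The SAP states 90% power at a 26.5% reduction, whereas its inputs give 99.5% here. That is a separate matter. If events were so few that power really was 90% (444 events), losing 10% of them would leave 86.8%.

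**Step 4. A mixed rule.** Suppose late events count but event-free stoppers are still cut back to the last visit. With one rate of 8% per year and d = 20%, person-time per patient is 0.356/0.08 = 4.45 years. The time removed is 0.20 × 0.644 × 2.75 = 0.354 years. The apparent rate is 0.356/(4.45 − 0.354) = 8.7% per year, so the mixture has a bias of its own.

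**The case against.** The best defence is that the sections can be read together: known events always count under the survival-time formula in 7.1, and last-visit censoring in 8.2.1 is for patients about whom nothing later is known. That may have been the intention, but 8.2.1 does not say so. Its wording is "Patients who prematurely discontinue their follow-up visits prior to the development of primary composite outcomes will be censored as of their last completed follow-up visit", which also describes a patient whose event comes after visits stop. Even on the kinder reading, last visit and last contact still disagree for event-free patients, and Step 4 shows that this matters. The defence does show that loss of known events follows from a literal reading and is not a settled consequence.

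Several stronger readings are tempting, and the documents do not support them.

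- *That the analysis is no longer ITT.* Section 4.1 governs who is analysed and in which arm. Patients censored early stay in, as randomised. The rule departs from the spirit of analysing irrespective of duration of participation, but excludes no one.
- *That intolerance will make stopping differ by arm.* The later regimen lasts 40 to 80 days and the earlier one 60, against a mean follow-up of 5.5 years. SAP section 12 keeps patients in the study despite non-compliance. Stopping the drug is not stopping visits.
- *That 22 to 113 events are lost.* This comes from 2855 × 0.05 × (1 − exp(−0.06 × 2.75)) = 22 and 2855 × 0.20 × (1 − exp(−0.08 × 2.75)) = 113. It treats every stopper as event-free at stopping and every later event as found. The search in 7.1 is best-effort and subject to the patient's wishes.
- *That the hazard ratio would be seriously distorted.* One illustrative simulation, with stopping tied to prognosis and 1.4 times as frequent on benznidazole, moved a true HR of 1.00 only to about 0.98. Those inputs are assumptions, so this is no more than indicative.

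A further caution stands against the remedy itself: deaths reported passively after visits stop may reach the trial more readily than news of survival, so ascertainment can depend on the event.

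**Conclusion.** The inconsistency is real: 8.2.1 conflicts with 7.1 and 7.2 on the primary endpoint, and nothing resolves it. Read literally, 8.2.1 drops known primary events and known event-free time.

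The likely size is modest: about 2% to 9% of primary events under the stated assumptions, up to about 3 points of power at HR 0.80, and very little at the SAP's 26.5% reduction if the 8% yearly rate holds. Incomplete tracing would lower the share lost. A higher event rate among those who stop would raise it. The case rests on a primary-endpoint rule that is ambiguous and that could make censoring depend on prognosis. It does not rest on power or on a breach of the ITT population.

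**What to change.** Replace the last-visit sentence in 8.2.1 with the 7.1 rule, and settle it before database lock:

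- Count every ascertained primary event up to the end of study follow-up, whether or not visits continued. Use adjudicated events, or the investigator's assessment where adjudication is unavailable, as 8.2 already allows.
- Make this subject to any patient's refusal of further information gathering, as in 7.1.
- Censor event-free patients at the last date on which their primary-outcome status is known from any source: visit, telephone, physician, relative or record. This is slightly tighter than 7.1, where a bare laboratory date can end follow-up.
- State the end-of-follow-up date. The SAP describes study termination only by its mean time.
- Keep last-visit censoring as a sensitivity analysis, because of the passive-reporting problem, and report by arm how many patients stopped visits and how many events came afterwards.

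The cost is a short change to the SAP text and one extra sensitivity run. It needs no data beyond what 7.1 and 7.2 already ask sites to obtain.

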#### **1.6. Natural History of CCD**

Mortality in patients with CCD is primarily ascribed to sudden cardiac death, progressive heart failure and thromboembolic events Sudden cardiac death occurs in 55% to 65% of cases, progressive heart failure in 20 to 25% and stroke in 10% to 15%. Sudden death is more frequent in young patients with isolated segmental wall motion abnormalities, but its real frequency is probably underestimated particularly in rural areas. Reported causes of death in CCD vary widely depending on the population studied and duration of follow-up.

The experience reported on recent studies of the natural history of CCD in outpatient cohorts which included both rural and urban populations is informative.

Rassi et al. followed for a mean period of 7.9  $\pm$  3.2 years 424 patients with Chagas cardiomyopathy determined by a positive serology and either ECG or 2D-echo abnormalities. Approximately half of the subjects were asymptomatic at baseline, palpitations and dyspnea being the most frequent clinical manifestations. Eighty one per cent of patients were in NYHA class I, and another 15% in Class II/III. A wide range of ECG abnormalities was documented, but complete right bundle branch block, left fascicular anterior block, and ventricular premature beats were the most frequent findings, detected in 40%, 37.5%, and 37.3% of the patients, respectively. Advanced ( $\geq 2^{nd}$  degree) AV block occurred in 4.2% of cases only. Echocardiogram was available at baseline in 354 patients and normal left ventricular function was described in 52%, with global dysfunction ranging from mild to severe in 41%. Apical aneurysm was reported in 10.5% of the cases and an intracavitary thrombus was identified in 1.7%. Holter monitoring documented frequent ventricular premature complexes (> 1000/24 hrs) in 45% as well as nonsustained ventricular tachycardia in 46% of the patients.

There were 130 deaths (31%) of which cardiovascular deaths accounted for 88%. The primary cause of cardiovascular death was sudden cardiac death (71%), progressive heart failure (18%) and thromboembolic events(10%). Multivariate Cox analysis identified six independent predictors of mortality: male gender, NYHA functional class III/IV, low QRS voltage, cardiomegaly on the chest x-ray, left ventricular dysfunction on the echocardiogram, and non-sustained ventricular tachycardia on Holter monitoring.

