#### 4.2.3 Method of assigning patients to treatment group

The patient identification (ID) and treatment numbers will be provided at randomization by a centralized randomization service located at the Brazilian Coordinating Center. A system similar to that used in the CREATE and HOPE trials conducted by the PHRI will be designed. Alterbatively if all sites have access to a computer with internet access, local randomization may be performed in a secure way. Randomization will be 1:1 with stratification according to centre using a random block size. Subsequent treatment numbers for study drug re-supply will be provided.

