In BENEFIT, Chagasic patients aged  $\geq 18$  years and  $\leq 75$  years, are eligible if, in addition to having any combination of at least 2 positive serologic tests for CD (indirect immunofluorescence, indirect hemagglutination, or ELISA), have evidence of cardiomyopathy based on the criteria outlined in Table I. Consenting patients who fulfill the eligibility criteria are randomized to receive benznidazole(BNZ) (5 mg/kg per day) or matched placebo for 60 days (randomized from November 2004 to December 2008 with 1543 patients ) or a maximum daily dose of 300mg for 60 days if weight was 60kg,, 70 days if weight was 70kg, and so on, to a maximum of 80 days(randomized from January 2009 to October 2011 with 1312 patients). (The reason for this was related with drug supply). The primary outcome is the composite of death; resuscitated cardiac arrest; sustained ventricular tachycardia(VT); new insertion of pacemaker or cardiac defibrillator; cardiac transplantation; and development of new heart failure, stroke, or systemic or pulmonary thromboembolic events. The average follow-up time will be 5.5 years, the sample size is 2753 patients pts with and the trial has a 90% power to detect a 26.5% relative risk reduction, assuming a yearly event rate of 8% in the control group of the composite primary outcome.

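### The primary log-rank and Cox analysis uses neither the centre stratification nor baseline prognostic factors: it is valid, but gives up some power, mostly through the covariates

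*Supplement*

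**What the plan says.** - **Allocation** (protocol 4.2.3): "Randomization will be 1:1 with stratification according to centre using a random block size". Protocol 7 expects 75 centres.
- **Primary analysis** (SAP 8.2.1): time to first component, with the arms' curves "compared using a logrank test. Treatment comparison based on Cox proportional hazard model will be reported as hazard ratio (HR". No stratification factor or covariate is named. Covariates enter a Cox model of this outcome only in the interaction tests of SAP 10.
- **Sensitivity analyses** (SAP 4 and 11): analyses in the two dosing-regimen cohorts, and one that changes which events count for patients with certain histories. None is covariate-adjusted.
- **Secondary outcomes** (SAP 8.2.2): adjusted logistic models are planned as well as the unadjusted ones.
- **Prognosis** (protocol 1.6): in a cohort of 424 patients, "Multivariate Cox analysis identified six independent predictors of mortality: male gender, NYHA functional class III/IV, low QRS voltage, cardiomegaly on the chest x-ray", plus left ventricular dysfunction on echo and non-sustained VT on Holter.
- **Baseline data** (SAP 5): the list includes gender, NYHA class, ECG, cardiothoracic ratio and LVEF.
- **Level and power** (SAP 8.2 and 2): "A two-sided significance level of 0.05 will be used for overall analysis", and "the trial has a 90% power to detect a 26.5% relative risk reduction". No adjustment is mentioned in the power statement.

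**The concern.** When randomisation is stratified, the usual practice is to analyse by the same strata. When strong baseline predictors are known and recorded, adjusting a time-to-event analysis for them usually raises power. This plan does neither for the outcome on which the trial's claim rests, yet it adjusts secondary outcomes. Eligibility runs from two minor ECG abnormalities to LVEF below 50%, with only NYHA IV or decompensated failure excluded, so a material spread of baseline risk is plausible.

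At stake is the chance of detecting a moderate effect such as the protocol's 20% reduction. If no adjusted analysis of the primary outcome is fixed in advance, any later one will be post hoc, which matters most if the result is borderline.

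**Working it through.** **1. Inputs from the documents.** SAP 2: "the sample size is 2753 patients pts with and the trial has a 90% power"; "assuming a yearly event rate of 8% in the control group of the composite primary outcome"; "The average follow-up time will be 5.5 years"; a 26.5% reduction, so HR 0.735. Two-sided 0.05; 1:1 within 75 centres. Protocol 4.1 targets a 20% reduction, so HR 0.80 is also examined.

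**2. The plan's own power figure.**
- Events: D = N × [2 − exp(−λT) − exp(−λ·HR·T)] / 2. With N = 2753, λ = 0.08, T = 5.5, HR = 0.735, D = 870. Reading 8% as an annual risk (λ = 0.0834) gives 900.
- Power: Φ(½√D·|ln HR| − 1.96) = 99.5% to 99.6%, not 90%.
- Events needed for 90%: 4 × (1.960 + 1.282)² / (ln 0.735)² = 444.

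The stated 90% therefore does not follow from its own inputs. That is a separate matter. Here it means only that at HR 0.735 there is ample power to start from. At HR 0.80 the same inputs (λ = 0.08) give D = 898 and power 91.7%.

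**3. Inputs that must be assumed.** The documents give no hazard ratios for the predictors and no between-centre variance. Assumed: prognostic-score SD 0 to 1.0 and centre SD 0 to 0.5, both on the log-hazard scale.

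**4. Simulation.** 2753 patients, 75 centres, permuted blocks of 4 within centre, control risk calibrated to 8% a year over 5.5 years. There were 1,500 runs per scenario at HR 0.80, 1,000 at 0.735 and 3,000 under the null. With no heterogeneity at HR 0.80 it returned 897 events and 91.8% power, matching step 2.

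Unadjusted Cox against centre-stratified and covariate-adjusted Cox, centre SD 0.3:

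| Conditional HR | Score SD | Events | HR unadjusted / adjusted | Power unadjusted / adjusted | Loss (points) | Formula power at unadjusted HR |
|---|---|---|---|---|---|---|
| 0.80 | 0.5 | 905 | 0.810 / 0.799 | 89.7% / 92.3% | 2.6 | 88.7% |
| 0.80 | 0.8 | 909 | 0.821 / 0.798 | 84.4% / 92.3% | 7.9 | 84.5% |
| 0.80 | 1.0 | 914 | 0.832 / 0.798 | 80.0% / 92.3% | 12.3 | 79.4% |
| 0.735 | 0.5 | 876 | 0.746 / 0.732 | 99.2% / 99.8% | 0.6 | 99.1% |
| 0.735 | 0.8 | 884 | 0.766 / 0.737 | 97.5% / 99.4% | 1.9 | 97.7% |
| 0.735 | 1.0 | 891 | 0.780 / 0.737 | 95.9% / 99.4% | 3.5 | 96.0% |

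The last column puts the unadjusted HR and the event count into the step 2 power formula. It agrees with the simulated unadjusted power to within about a point, so the loss is that of testing a marginal HR nearer 1.

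**5. Centre alone** (score SD 0). At HR 0.80, stratifying raises power from 91.5% to 92.5% (centre SD 0.3) and from 89.1% to 91.0% (SD 0.5), and moves the HR by at most 0.008. At HR 0.735 with SD 0.5, power is 99.1% either way. A separate simulation with centre SD 0.3 to 0.7 gave changes of −0.3 to +3 points.

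**6. Covariates alone** (centre SD 0, HR 0.80). Power rises from 88.5% to 92.4%, from 84.5% to 91.3% and from 76.6% to 91.0% for score SD 0.5, 0.8 and 1.0.

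**7. Type I error of the unadjusted analysis.** 4.5% (score SD 0.8, centre SD 0.3) and 4.7% (centre SD 0.5 alone).

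**8. Fewer events.** A separate simulation with 2,855 patients, HR 0.80 and about 670-730 events gave 80% against 85% (score SD 0.6) and 74% against 82% (SD 0.9). That event count fits the low end of the protocol's 6%-8% a year: 2855 × [2 − exp(−0.33) − exp(−0.264)] / 2 = 732.

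Monte Carlo error is about 0.3 to 1 point throughout.

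**9. Reported predictors against the SAP 5 list.**

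| Predictor (protocol 1.6) | SAP 5 |
|---|---|
| Male sex | listed |
| NYHA III/IV | class listed (class IV is excluded from the trial) |
| LV dysfunction | LVEF listed |
| Cardiomegaly on X-ray | cardiothoracic ratio, cut at 0.59 (eligibility uses 0.50) |
| Low QRS voltage | ECG listed, this finding not named |
| Holter non-sustained VT | not listed |

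**The case against.** The strongest reply is that nothing here is an error. Under 1:1 randomisation an unadjusted log-rank and Cox analysis is valid, and the protocol summary had already named the log-rank test. That stands, and it rules out several stronger readings that a reader might infer:

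- **That the HR is biased.** The shift towards 1 is non-collapsibility: the marginal and conditional HRs are different quantities.
- **That ignoring the strata invalidates the test.** Type I error is held or slightly conservative.
- **That the trial falls short of its planned power.** The SAP's power statement assumes no adjustment, so nothing promised is lost.
- **That the mid-trial regimen change is ignored.** SAP 4 plans sensitivity analyses in both cohorts (1543 and 1312 patients). Each is defined by randomisation date and has concurrent placebo patients.
- **That all the predictors are on file for everyone.** The summary's schedule sets baseline ECG and echo for all patients but lists no chest X-ray, and the SAP list does not name low QRS voltage.

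It is also fair that the reported factors predict death rather than the composite, and that a second cohort in protocol 1.6 names others (QT dispersion and LV end-systolic dimension), which SAP 5 does not list. This argues for a short covariate list. SAP 10 does fit models with gender, country and LV function, but as interaction tests; they give no adjusted primary estimate. The omission therefore remains.

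**Conclusion.** The point holds as a matter of efficiency. SAP 8.2.1 leaves out the randomisation stratum and the known baseline predictors, and no adjusted analysis of the primary outcome is planned anywhere. Its conclusions would be valid but less powerful than the data allow.

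The size depends on assumed SDs and cannot be derived from the documents. In the simulation the adjusted model recovers the conditional HR, so the score SD should be read as the part of risk that the chosen covariates explain; weak covariates put the trial at the low end. The loss matters if the true effect is near 0.80 and is small at 0.735. The case for using centre is consistency with the design more than power. This is a recommended improvement to the plan.

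**What to change.** Before unblinding, amend SAP 8.2.1 as follows:

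1. Stratify the primary log-rank test and Cox model by centre, pooling small centres within country by a rule fixed in advance.
2. Adjust the Cox model for sex, NYHA class and LVEF, stating how each is coded.
3. Add cardiothoracic ratio and low QRS voltage only if they are recorded for essentially all patients, and only after the 0.59 cut-off in SAP 5 and the 0.50 in SAP Table I are reconciled.
4. Report the unadjusted HR alongside, and say that the adjusted HR is conditional.
5. Provide a missing-value category for covariates. SAP 7.2 rules out imputation, so without one a patient lacking a value could drop out of the model.

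A dosing-regimen stratum is optional.

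The cost is wording: SAP 2 allows blinded revision until sign-off before database lock, and the three core covariates are already in the baseline list. The downsides are the missing category for a few patients and a conditional rather than marginal HR as the headline estimate.
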